3.1.1.3. Antipyretic/Analgesic Medication

The use of antipyretic medications to treat pain symptoms or fever associated with study intervention administration will be recorded in the reactogenicity e-diary daily during the 7-day reporting period or longer for ongoing symptoms. For the use of antipyretic medication from Day 1 through Day 7 after vaccination, the following endpoints and variables will be derived for analysis following the same rules as for local reactions (see Section 3.1.1.1), where applicable:

- Presence (yes or no) of use of antipyretic medication on each day (Day 1 through Day 7)
- Presence (yes or no) of use of antipyretic medication on any day (Day 1 through Day 7)
- Duration (first to last day reported) of use of antipyretic medication
- Onset day of use of antipyretic medication

The use of antipyretic medication will be summarized and included in the systemic event summary tables but will not be considered a systemic event.

3.1.1.4. Adverse Events

AEs will be collected from the time the participant provides informed consent through and including Visit 2 (approximately 4 weeks after vaccination). In addition, any AEs occurring up to 48 hours after any subsequent blood draw must be recorded on the CRF. AEs will be categorized according to MedDRA terms. Missing AE start dates will be imputed following the Pfizer data standard rules as described in Section 5.3.

The safety primary endpoint "AEs from vaccination through 4 weeks after vaccination" and other AE endpoints will be summarized by SOC and PT.

These primary endpoints will be supported by summaries and/or listings of related AEs, severe or life-threatening AEs, immediate AEs (within the first 30 minutes after the study vaccination), and AESIs (defined in Section 8.4.8 of the protocol).

3.1.1.5. Serious Adverse Events

SAEs will be collected from the time the participant provides informed consent through the duration of the study (approximately 6 months after vaccination). SAEs will be categorized according to MedDRA terms. The safety primary endpoint "SAEs from vaccination through 6 months after vaccination" will be summarized, by SOC and PT, at the participant level for each group. Additionally, all SAEs will be presented in the listing.

3.1.2. Immunogenicity Primary Endpoints

- SARS-CoV-2 Omicron (XBB.1.5)—neutralizing titers at 4 weeks after vaccination
- HAI titers against the seasonal strains recommended by WHO for the northern hemisphere 2023-2024 influenza season at 4 weeks after vaccination

The 4 influenza virus strains recommended by WHO are: A/West Virginia/30/2022 (A/Wisconsin/67/2022 pdm09-like virus) (H1N1), A/Darwin/6/2021 (H3N2), B/Austria/1359417/2021, and B/Phuket/3073/2013.

3.2. Secondary Endpoint(s)

Not applicable.

3.3. Other Safety Endpoints

Local reactions, systemic events, AEs, and SAEs have been described above in the Safety Primary Endpoints section (Section 3.1.1).

3.4. Exploratory Endpoints

- SARS-CoV-2 Omicron (XBB.1.5)—neutralizing titers and HAI titers against the seasonal strains recommended by WHO for the northern hemisphere 2023-2024 influenza season at 6 months after vaccination
- SARS-CoV-2 neutralizing titers and/or HAI titers for variants (under monitoring, of interest, and/or of concern) not already specified
- HAI titers measured by virus microneutralization assays for the seasonal strains recommended by WHO

3.5. Baseline Variables

Measurements or samples collected prior to the study vaccination are considered the baseline data for the assessments.

3.5.1. Demographics, Medical History, and Physical Examination

Demographic variables will be collected, including age (in years), sex (male or female), race (Black or African American, American Indian or Alaska Native, Asian, Native Hawaiian or other Pacific Islander, White, multiracial, unknown, and not reported), ethnicity (Hispanic/Latino or of Spanish origin, non-Hispanic/non-Latino or not of Spanish origin, and not reported), and BMI. In cases where more than 1 category is selected for race, the participant would be counted under the category "multiracial" for analysis.

Medical history will be collected and categorized according to the current version (at the time of reporting) of MedDRA.

If the clinical assessment indicates that a physical examination is necessary to comprehensively evaluate the participant, a physical examination will be performed. Physical examination findings collected during the study will be considered source data and will not be required to be reported, unless otherwise noted.

3.5.2. E-Diary Transmission

An e-diary will be considered transmitted if any data for the local reactions, systemic events, or use of antipyretic/analgesic medication are present for any day. If all data are missing for all the items on the e-diary for all 7 days after vaccination, the e-diary will be considered not transmitted.

3.5.3. Prior/Concomitant Vaccines and Concomitant Medications

The following prior and concomitant medications and vaccinations will be recorded in the CRF:

- Any COVID-19 vaccine from 12 months prior to enrollment until the last visit (Visit 3).
- Licensed or investigational influenza vaccine from 12 months prior to enrollment until the last visit (Visit 3).
- Any vaccinations received from 28 days prior to Visit 1 until the last visit (Visit 3).
- Details of any concomitant medication taken to treat fever or pain (solicited reactogenicity symptoms) as reported in the e-diary will be collected.
- Prohibited medications specified in Section 6.9.1 of the protocol.

Prior and concomitant vaccines and concomitant and prohibited medications will be coded using the WHO Drug Dictionary.

4. ANALYSIS SETS (POPULATIONS FOR ANALYSIS)

Analysis populations are defined for the statistical analysis of safety and immunogenicity results in the table below. Data for all participants will be assessed to determine if participants meet the criteria for inclusion in each analysis population prior to releasing the database, and classifications will be documented per standard operating procedures.

| Participant Analysis Set | Description | |
|------------------------------|---|--|
| Screened | All participants who have a signed ICD. | |
| Randomized | All participants who are assigned a randomization number in the IRT system. | |
| Safety | All participants who receive at least 1 dose of the study intervention. | |
| Evaluable immunogenicity | All eligible assigned participants who receive the study intervention to which they are assigned, have at least 1 valid and determinate immunogenicity result from the blood sample collected within 27 to 42 days after vaccination, and have no other important protocol deviations as determined by the clinician. | |
| All-available immunogenicity | All assigned participants who receive the study intervention and have 1 valid and determinate immunogenicity result after vaccination. | |

Important protocol deviations will be determined by the clinician. An important protocol deviation is a protocol deviation that, in the opinion of the sponsor's clinician, would materially affect assessment of immunogenicity, eg, participant receipt of a prohibited vaccine or medication that might affect immune response or a medication error with suspected decrease in potency of the vaccine. The sponsor's medical monitor will identify those participants with important protocol deviations that result in exclusion from analysis populations.

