5.2. General Methods

Other than the IRC review of early Phase 1 safety data before the initiation of Phase 2 enrollment, data from Phase 1 and Phase 2 participants will be combined for the safety and immunogenicity analyses.

CIs for all endpoints in the statistical analysis will be presented as 2-sided at the 95% level unless specified otherwise.

The safety analyses are based on the safety population. Participants will be summarized by vaccine group according to the study interventions they actually received.

For all the immunogenicity endpoints, the analysis will be based on the evaluable immunogenicity population. An additional analysis may be performed based on the all-available immunogenicity population if there is a $\geq 10\%$ difference in sample size between the all-available immunogenicity population and the evaluable immunogenicity population. Participants will be summarized according to the vaccine group to which they were randomized.

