5.2.2.3. Geometric Mean Fold Rises

GMFRs are defined as ratios of the results after vaccination to the results before vaccination. GMFRs are limited to participants with nonmissing values at both time points. GMFRs will be calculated as the mean of the difference of logarithmically transformed assay results (later time point minus earlier time point) and exponentiating the mean. The associated 2-sided 95% CIs will be obtained by constructing CIs using the Student t distribution for the mean difference on the logarithm scale and exponentiating the confidence limits.

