6.1.2. Immunogenicity Primary Endpoints

6.1.2.1. SARS-CoV-2 Omicron (XBB.1.5)-Neutralizing Titers

6.1.2.1.1. Main Analysis

- Estimands:
 - o GMTs of SARS-CoV-2 Omicron (XBB.1.5)—neutralizing titers before vaccination and at 4 weeks after vaccination.
 - O GMFRs of SARS-CoV-2 Omicron (XBB.1.5)—neutralizing titers from before vaccination to 4 weeks after vaccination.
 - o Percentages of participants with seroresponse to SARS-CoV-2 Omicron (XBB.1.5) at 4 weeks after vaccination.
- Analysis set: Evaluable immunogenicity population, all-available immunogenicity population (as applicable) (Section 4).
- Analysis time point: 4 Weeks after vaccination.
- Analysis methodology: The GMTs and the associated 2-sided 95% CIs will be provided for each vaccine group using the statistical methods described in Section 5.2.2.1. The GMFRs and the associated 2-sided 95% CIs will be provided for each vaccine group using the statistical methods described in Section 5.2.2.3. The percentages of participants with seroresponse and the associated Clopper-Pearson 95% CIs will be provided for each vaccine group (Section 5.2.1). Seroresponse is defined as achieving a ≥4-fold rise from

baseline (before the study vaccination). If the baseline measurement is below the LLOQ, the postvaccination measure of \geq 4 × LLOQ is considered seroresponse.

- Intercurrent events and missing data: Serology data deemed unevaluable because of noncompliance with the key protocol criteria will be excluded. Missing data will not be imputed.
- Reporting results: GMTs before vaccination and at 4 weeks after vaccination, GMFRs from before vaccination to 4 weeks after vaccination, and percentages of participants with seroresponse to SARS-CoV-2 Omicron (XBB.1.5) at 4 weeks after vaccination, along with the associated 2-sided 95% CIs, will be provided for each vaccine group.

Figures:

Empirical RCDCs and bar charts of GMTs and the associated 2-sided 95% CIs will be provided for SARS-CoV-2 Omicron (XBB.1.5)—neutralizing titers before and 4 weeks after vaccination for each vaccine group.

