6.4. Exploratory Endpoints

6.4.1. SARS-CoV-2 Omicron (XBB.1.5)-Neutralizing Titers and HAI Titers

- Estimands:
 - GMTs of SARS-CoV-2 Omicron (XBB.1.5)—neutralizing titers and strain-specific HAI titers before vaccination and at 6 months after vaccination.
 - O GMFRs of SARS-CoV-2 Omicron (XBB.1.5)—neutralizing titers and strain-specific HAI titers from before vaccination to 6 months after vaccination.
 - o Percentages of participants with seroresponse to SARS-CoV-2 Omicron (XBB.1.5) and achieving strain-specific HAI seroconversion at 6 months after vaccination.
 - o Percentages of participants with strain-specific HAI titers ≥1:40 before vaccination and at 6 months after vaccination.
- Analysis set, analysis methodology, and intercurrent events and missing data are the same as described above for the immunogenicity primary endpoints (Section 6.1.2).
- Reporting results: GMTs before vaccination and at 6 months after vaccination, GMFRs from before vaccination to 6 months after vaccination, percentages of participants with seroresponse to SARS-CoV-2 Omicron (XBB.1.5) at 6 months after vaccination, percentages of participants achieving HAI seroconversion at 6 months after vaccination, and percentages of participants with HAI titers ≥1:40 before vaccination and at 6 months after vaccination, along with the associated 2-sided 95% CIs, will be provided for each vaccine group. This analysis may be conducted in a selected subset of participants.

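### The only evaluable immunogenicity set requires a day 27-42 result and is reused at 6 months, so valid 6-month titers are dropped for want of a 4-week sample that those estimates do not use

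*SAP*

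**What the plan says.** SAP section 4 gives one evaluable immunogenicity population. Besides eligibility, receipt of the assigned intervention and no other important deviation, members must "have at least 1 valid and determinate immunogenicity result from the blood sample collected within 27 to 42 days after vaccination". No other sampling window appears in the definition. Protocol 9.2 left the window unspecified, so the number comes from the SAP.

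SAP 5.2 then states: "For all the immunogenicity endpoints, the analysis will be based on the evaluable immunogenicity population". For the 6-month titers, SAP 6.4.1 says: "Analysis set, analysis methodology, and intercurrent events and missing data are the same as described above for the immunogenicity primary endpoints". The 6-month outputs it lists include "GMTs before vaccination and at 6 months after vaccination, GMFRs from before vaccination to 6 months after vaccination", together with seroresponse, seroconversion and the percentage with HAI titers of at least 1:40. It adds: "This analysis may be conducted in a selected subset of participants".

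Three further rules matter:
- SAP 5.2.2.3, on fold rises: "GMFRs are limited to participants with nonmissing values at both time points".
- SAP 6.1.2, on handling of results, carried to 6 months by 6.4.1: "Serology data deemed unevaluable because of noncompliance with the key protocol criteria will be excluded".
- SAP 5.2, on the wider population: "An additional analysis may be performed based on the all-available immunogenicity population". The condition is a difference in sample size of at least 10% between the two populations.

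The Schedule of Activities (protocol 1.3) places Visit 2 at 28-35 days and Visit 3 at 175-189 days. The Visit 3 window does not appear in any analysis-set definition.

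**The concern.** Membership of the set is decided by the 4-week sample, but the 6-month estimates are built from baseline and 6-month values only. Someone who misses Visit 2 and returns for Visit 3 gives a usable 6-month titer that the main analysis sets aside for a reason unrelated to that measurement.

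The definition is also silent in the other direction. With no 6-month window, nothing in it says which Visit 3 draws count as on time.

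At stake are some precision, and possibly some selection of participants, in the 6-month summaries. There is no hypothesis test in this study, so no error rate is involved.

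**Working it through.** **Tracing one participant.** Take someone eligible, vaccinated as assigned, with no important deviation, a valid baseline result, no sample in days 27-42, and a valid result at day 180.
1. SAP 4: no qualifying 4-week result, so not in the evaluable set.
2. SAP 5.2 and 6.4.1: the 6-month analysis uses that set, so this participant is out.
3. SAP 5.2.2.3: the 6-month fold rise needs only the baseline and 6-month values, and both are present. The 6-month GMT and response rates likewise use no 4-week value.
4. SAP 6.1.2: the result-level rule removes unevaluable serology. It cannot restore a participant who is already outside the set.

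**How narrow the routes are.** Days 27-42 allow one day earlier and seven days later than the Visit 2 window of 28-35, so a modestly late draw still qualifies. One valid and determinate result is enough. Protocol 8.2 lists XBB.1.5 neutralization and HAI for four strains, so an indeterminate result excludes a participant only when nothing from that sample is valid.

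**Inputs for size.** Per group: 20 in Phase 1 + 140 in Phase 2 = 160, and 4 × 160 = 640 as stated. The plan's one sizing figure, in protocol 9.5, reproduces: 1 − 0.99^160 = 0.7997 against the stated 80%. It concerns adverse events and does not bear on this point. No missing-sample rate is given, so the rate is an assumption: 2%, 5% or 10% of the group lack a qualifying 4-week result but have a 6-month result.

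**Formula.** For a log-scale mean with unchanged SD, the ratio of 95% CI half-widths is [t(0.975, n−1)/√n] ÷ [t(0.975, N−1)/√N].

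With N = 160, the denominator is 1.9750/√160 = 0.15614:

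| Assumed rate | Lost | n kept | t/√n | Ratio |
|---|---|---|---|---|
| 2% | 3 | 157 | 0.15765 | 1.010 |
| 5% | 8 | 152 | 0.16026 | 1.026 |
| 10% | 16 | 144 | 0.16472 | 1.055 |

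For a response rate of 50%, the Clopper-Pearson half-width goes from 8.00 points (80/160) to 8.21 (76/152) and 8.44 (72/144).

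**Sensitivity to N, at 5% and 10%.** If only 144 per group have 6-month results, 7 and 14 are lost, with ratios 1.026 and 1.053. If a subset of 80 per group is analyzed, 4 and 8 are lost, with ratios 1.027 and 1.056. The relative widening hardly depends on N.

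**The 10% condition.** SAP 5.2 does not say which population is the denominator, or whether the comparison is per group or pooled. For 15 lost of 160, the difference is 15/160 = 9.4% of the all-available set but 15/145 = 10.3% of the evaluable set. No exact cut-off can be derived from the text.

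**The case against.** The best defense is that a single cohort is a legitimate choice: it keeps the 4-week and 6-month summaries on one base population, and the protocol lets the SAP settle such details. No two passages contradict each other. That much stands. But the SAP gives no such rationale, and a common cohort is not secured anyway, since evaluable participants who miss Visit 3 still drop out at 6 months.

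The second defense is size. The endpoints are exploratory and descriptive, the rates above are assumed, participants who leave the study have no 6-month result to lose, and SAP 6.4.1 already allows a subset. This stands, and it is why the point is minor.

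The third is that the all-available analysis picks these participants up. It would include them, and a reader who infers that it runs with no exclusion for noncompliance would be wrong: the set definition has none, but the result-level rule in SAP 6.1.2 is stated for both populations. It remains optional and conditional, however, and the planned 6-month estimand is in evaluable participants.

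A reader might also infer that any late or indeterminate 4-week sample costs a participant the 6-month analysis. The wider window and the one-valid-result rule do not support that.

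**Conclusion.** The gap is real on the text and minor in effect. As written, the main 6-month analysis excludes participants who have valid baseline and 6-month results but no valid result of any kind from days 27-42, and no 6-month sampling window is set.

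If 2-10% of 160 per group are in that position, 3-16 results per group are lost and log-scale intervals are about 1.0-5.5% wider. This assumes an unchanged SD and that everyone counted attends Visit 3, so it is an upper range for those rates. The documents give no basis for stating a direction of any selection effect.

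Two stronger readings are not supported. The primary 4-week results are untouched, because the 27-42 day requirement suits them. Nor can it be said that a loss below some exact count would leave the all-available analysis untriggered, since the denominator of the 10% condition is not stated.

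**What to change.** In SAP section 4, add a separate 6-month evaluable immunogenicity set whose members:
- are eligible and received the intervention to which they were assigned;
- have at least one valid and determinate result from a sample within a numeric 6-month window, fixed before analysis and including at least the protocol's days 175-189;
- have no other important protocol deviation up to that draw;
- need no 4-week sample.

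Point SAP 6.4.1 to this set. Leave the 4-week set unchanged, including its deviation rule. That rule carries no date limit, so rewriting it by date would alter the primary population, which this point gives no reason to do.

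The cost is SAP wording and one extra population flag, with no new data or participants. The small downside is that the 4-week and 6-month summaries will not rest on exactly the same participants, which a footnote with the counts can make plain. Settling this before the 6-month analysis also avoids choosing a population after results are visible in a sponsor-unblinded study.

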5. GENERAL METHODOLOGY AND CONVENTIONS

5.1. Hypotheses and Decision Rules

There is no statistical hypothesis specified in this study. All statistical analyses will be descriptive.

5.2. General Methods

Other than the IRC review of early Phase 1 safety data before the initiation of Phase 2 enrollment, data from Phase 1 and Phase 2 participants will be combined for the safety and immunogenicity analyses.

CIs for all endpoints in the statistical analysis will be presented as 2-sided at the 95% level unless specified otherwise.

The safety analyses are based on the safety population. Participants will be summarized by vaccine group according to the study interventions they actually received.

For all the immunogenicity endpoints, the analysis will be based on the evaluable immunogenicity population. An additional analysis may be performed based on the all-available immunogenicity population if there is a $\geq 10\%$ difference in sample size between the all-available immunogenicity population and the evaluable immunogenicity population. Participants will be summarized according to the vaccine group to which they were randomized.

5.2.1. Analysis for Binary Data

Descriptive statistics for categorical variables (eg, proportions) are the percentage (%), the numerator (n) and the denominator (N) used in the percentage calculation, and the 95% CIs, where applicable.

The exact 95% CI for binary endpoints for each group will be computed using the F distribution (Clopper-Pearson method). The 95% CI for the between-group difference for binary endpoints will be calculated using the Miettinen and Nurminen method. 2

The primary approach to calculate the difference in seroresponse rate or seroconversion rate between the 2 vaccine groups and the associated 95% CI will be based on the Miettinen and Nurminen method stratified by baseline neutralizing titer category (< median, \geq median) and age group (50 through 64 years of age, \geq 65 years of age). The median of baseline neutralizing titers will be calculated based on the pooled data in the 2 comparator groups.

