#### 8.2. Efficacy and/or Immunogenicity Assessments

Samples will be collected at the time points specified in the SoA from all participants and the following assays will be performed:

- SARS-CoV-2 neutralization assays (Omi XBB.1.5).
- HAI titers (from HAI based on cell-derived virus) for the seasonal strains (2×A, 2×B) recommended by WHO.

To describe the immune response to emerging variants of SARS-CoV-2 and/or influenza, additional assay may be run on an exploratory basis.

Virus microneutralization assays may be run on all or a subset of samples on an exploratory basis as detailed in the SAP.

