5.2.2.2. Geometric Mean Ratios

Model-Based GMR:

The GMR and the associated 95% CI will be calculated by exponentiating the difference in LS means and the corresponding CIs based on analysis of logarithmically transformed assay results using a linear regression model that includes terms for baseline assay results (log scale), age, and comparison group.

Unadjusted GMR:

The GMR will be calculated as the mean of the difference of logarithmically transformed assay results and exponentiating the mean. Two-sided CIs will be obtained by calculating CIs using the Student t distribution for the mean difference of the logarithmically transformed assay results and exponentiating the confidence limits.

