6.1.2.2. HAI Titers

6.1.2.2.1. Main Analysis

- Estimands:
 - o GMTs of strain-specific HAI titers before vaccination and at 4 weeks after vaccination.
 - o GMFRs of strain-specific HAI titers from before vaccination to 4 weeks after vaccination.

- Percentages of participants achieving strain-specific HAI seroconversion at 4 weeks after vaccination.
- o Percentages of participants with strain-specific HAI titers ≥1:40 before vaccination and at 4 weeks after vaccination.
- Analysis set: Evaluable immunogenicity population, all-available immunogenicity population (as applicable) (Section 4).
- Analysis time point: 4 Weeks after vaccination.
- Analysis methodology: The GMTs and the associated 2-sided 95% CIs will be provided for each vaccine group using the statistical methods described in Section 5.2.2.1. The GMFRs and the associated 2-sided 95% CIs will be provided for each vaccine group using the statistical methods described in Section 5.2.2.3. The percentages of participants achieving HAI seroconversion and with HAI titers ≥1:40 and the associated Clopper-Pearson 95% CIs will be provided for each vaccine group (Section 5.2.1). Seroconversion is defined as an HAI titer <1:10 prior to vaccination and ≥1:40 at the time point of interest, or an HAI titer of ≥1:10 prior to vaccination with a minimum 4-fold rise at the time point of interest.
- Intercurrent events and missing data: Serology data deemed unevaluable because of noncompliance with the key protocol criteria will be excluded. Missing data will not be imputed.
- Reporting results: For each influenza virus strain, GMTs before vaccination and at 4 weeks after vaccination, GMFRs from before vaccination to 4 weeks after vaccination, percentages of participants achieving HAI seroconversion at 4 weeks after vaccination, and percentages of participants with HAI titers ≥1:40 before vaccination and at 4 weeks after vaccination, along with the associated 2-sided 95% CIs, will be provided for each vaccine group.

Figures:

Empirical RCDCs and bar charts of GMTs and the associated 2-sided 95% CIs will be provided for each strain-specific HAI titer before and 4 weeks after vaccination for each vaccine group.

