6.1.2.2.2. Supportive Analysis

The model-based and unadjusted GMRs of strain-specific HAI titers at 4 weeks after vaccination and the associated 95% CIs will be calculated using the statistical methods described in Section 5.2.2.2 for the following comparative groups:

• BNT162b2 (Omi XBB.1.5)/RIV and placebo (Group 1) vs BNT162b2 (Omi XBB.1.5) and RIV (Group 2).

- BNT162b2 (Omi XBB.1.5)/RIV and placebo (Group 1) vs RIV and placebo (Group 4).
- BNT162b2 (Omi XBB.1.5) and RIV (Group 2) vs RIV and placebo (Group 4).

The adjusted and unadjusted difference in percentages of participants with HAI seroconversion at 4 weeks after vaccination and the associated 2-sided 95% CIs will be calculated using the statistical methods described in Section 5.2.1 for the same comparative groups listed above.

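### Adjusted HAI seroconversion differences are stratified by baseline neutralizing titer, not the strain's own baseline HAI titer, so they barely adjust for HAI baseline imbalance

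*SAP*

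**What the plan says.** SAP 5.2.1 gives a single rule. "The primary approach to calculate the difference in seroresponse rate or seroconversion rate between the 2 vaccine groups" is to be "based on the Miettinen and Nurminen method stratified by baseline neutralizing titer category" (below the median, or at or above it) and age group. The only cut point defined is for that assay: "The median of baseline neutralizing titers will be calculated based on the pooled data in the 2 comparator groups".

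SAP 6.1.2.2.2 refers "The adjusted and unadjusted difference in percentages of participants with HAI seroconversion at 4 weeks after vaccination" to Section 5.2.1 for Groups 1 vs 2, 1 vs 4 and 2 vs 4. With four strains that makes 3 × 4 = 12 adjusted differences. No HAI stratum is named.

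The endpoint itself uses the strain's baseline. In SAP 6.1.2.2.1, "Seroconversion is defined as an HAI titer <1:10 prior to vaccination" with at least 1:40 afterwards, or a baseline of at least 1:10 with at least a 4-fold rise.

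Protocol 8.2 lists SARS-CoV-2 neutralization and, as a separate assay, "HAI titers (from HAI based on cell-derived virus) for the seasonal strains". It adds that "Virus microneutralization assays may be run on all or a subset of samples on an exploratory basis".

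For the GMRs of the same contrasts, the model in SAP 5.2.2.2 has "terms for baseline assay results (log scale), age, and comparison group".

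SAP 2.1 lists no modifications to the protocol's analysis plan. Protocol 9.3.1.1 names the Miettinen and Nurminen method without strata.

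**The concern.** A stratified difference corrects for chance imbalance only in the stratum variables and whatever correlates with them. For HAI seroconversion the obvious prognostic variable is that strain's baseline HAI titer, and it is not a stratum. Of the two strata used, age group is already balanced by stratified randomization, and the neutralizing titer belongs to a different virus.

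Three things follow.

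- The estimate that the SAP calls its primary approach for these differences would carry an HAI imbalance almost as the unadjusted one does, while being labelled adjusted.
- The adjusted HAI GMR and the adjusted HAI seroconversion difference for the same pair of groups would control for different baselines.
- The HAI estimate depends on a second assay. The evaluable set needs only one valid result and missing serology is not imputed, so a participant with HAI results but no baseline SARS-CoV-2 titer has no stratum.

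The sponsor is unblinded and may review data during the study. An HAI stratum chosen later would be chosen with data in view.

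**Working it through.** **1. Can the text be read another way?** In the primary and supportive analyses, neutralizing titer means the SARS-CoV-2 XBB.1.5 assay. Reading it as influenza microneutralization does not help, because that assay is exploratory and may cover only a subset of samples. Where the SAP means each assay's own baseline (5.2.2.2), it says so in general terms; 5.2.1 does not.

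**2. The plan's own figures.** None is given for this adjustment. The only sample-size figure, in Protocol Table 7, reproduces: 1 − 0.99^160 = 0.7997 against 0.80. It serves here only to confirm about 160 per group.

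**3. Unadjusted shift.** With two baseline HAI levels, shift = (seroconversion gap between levels) × (imbalance in the share above the median). The gap is assumed. For a 10-point imbalance:

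- gap 10 points: 0.10 × 10 = 1.0 point
- gap 20 points: 2.0 points
- gap 30 points (70% vs 40%): 3.0 points
- gap 40 points: 4.0 points

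**4. What the neutralizing stratum removes.** The fraction removed is about φ², with φ = (2/π)·asin(ρ), where ρ is the correlation between the two baseline log titers (assumed). Simulation used 160 per arm, age balanced, no vaccine effect, and stratum weights n1·n0/(n1+n0). The results for the 30-point gap are:

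| ρ | φ² | removed, simulated | shift left, strata as written | shift left, own-HAI strata |
|---|---|---|---|---|
| 0 | 0.0% | 0.1% | 3.00 | 0.00 |
| 0.1 | 0.4% | 0.3% | 2.99 | 0.00 |
| 0.2 | 1.6% | 1.4% | 2.96 | 0.00 |
| 0.3 | 3.8% | 4.0% | 2.88 | 0.00 |
| 0.5 | 11.1% | 10.6% | 2.68 | 0.00 |

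The zeros in the last column hold by construction, because this model has only two HAI levels.

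**5. Less idealized models.**

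- *Discrete doubling-dilution HAI.* Nine scenarios of 4,000 trials, 144 evaluable per group (90% of 160, assumed), ρ = 0.1, gaps of 2 to 36 points. Shift per 10-point imbalance: 0.39–3.75 unadjusted, 0.39–3.72 with neutralizing strata, 0.01–0.41 with own-HAI strata. One further scenario at ρ = 0.3 gave 1.21 unadjusted and 1.19 with neutralizing strata.
- *A separate discrete-titer simulation, also 144 per group.* At a 24-point gap, the shift per 10-point imbalance was 2.4–2.6 points with neutralizing strata against 2.5–2.6 unadjusted. Own-HAI strata removed about 80–95% at gaps of 12 to 24 points. With no gap, neither stratification mattered.
- *Continuous titer, steeper gradient.* Own-HAI median strata removed about 50–60%. Neutralizing strata removed 0–4% for ρ up to 0.3, 17% at 0.5 and 38% at 0.7. With a weaker gradient the shift was under 1 point and neither choice mattered.

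**6. Scale.** At 65% seroconversion (assumed) and 144 per group, the half-width is 1.96 × √(2 × 0.65 × 0.35/144) = 0.110, or 11 points. The SD of the imbalance is √(2 × 0.25/144) = 0.059, so an imbalance of 10 points or more has a probability of about 0.09 per contrast (0.06–0.08 in the discrete simulation). At one SD, the shift left by the strata as written is 0.59 × (0.39 to 3.72) = 0.2 to 2.2 points.

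**7. Precision.** In the nine scenarios, the SD of the estimate relative to unadjusted was 1.001–1.005 with neutralizing strata and 0.934–1.004 with own-HAI strata. These are ratios of simulated SDs; Miettinen and Nurminen intervals were not computed.

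**The case against.** The best reply accepts the reading and disputes its importance. Between-group comparison is an exploratory objective, the HAI differences are supportive, and there is no hypothesis, margin or decision rule. The primary HAI estimands are per-group summaries and are untouched. The unadjusted difference and a GMR that does adjust for baseline HAI are reported alongside, and baseline HAI by strain and group would expose an imbalance. Chance imbalance is ordinary sampling variability that the interval already covers, so some precision is lost but not validity. A 10-point imbalance is uncommon, both the gap and the correlation are assumed, and own-HAI strata may remove only about half of the shift. The SAP also states its strata openly, and the mismatch may simply be carried over from the SARS-CoV-2 endpoint.

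All of this stands as a limit on consequence. None of it supplies an HAI stratum or gives the neutralizing stratum a purpose for an influenza endpoint. The availability of an unadjusted result does not justify an adjusted one that differs from it in name only.

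**Conclusion.** The concern holds. As written, the 12 adjusted HAI seroconversion differences use a baseline that has little bearing on the endpoint and omit the one that helps define it. For correlations up to about 0.3, the stratification removes at most about 4% of the shift from an HAI imbalance. A stronger correlation would remove more: about 11% at 0.5 in the two-level model.

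The absolute effect is modest: roughly 0.4 to 4 points for a 10-point imbalance, depending on the assumed gap, and close to nothing if seroconversion hardly depends on baseline. Randomization keeps the estimate unbiased on average. It should be corrected because the rule is stated, contradicts the SAP's own GMR adjustment, and is easy to put right before data are analyzed. It does not threaten the primary results.

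**What to change.** Separate the two endpoints in SAP 5.2.1, for example:

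> For SARS-CoV-2 seroresponse, strata are baseline SARS-CoV-2 neutralizing titer category (< median, ≥ median) and age group. For HAI seroconversion, strata are the baseline HAI titer category for that strain (≤ or > the pooled median of the two groups compared) and age group. If any stratum has fewer than 5 participants in either group, the HAI categories are collapsed and age group alone is used.

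Putting ties in the lower HAI category differs from the convention for neutralizing titers on purpose: if the median sits at the assay floor, a below-median category would be empty. The threshold of 5 is the sponsor's to choose, but it should be fixed before analysis. Each output should state which strata were used, because collapsing could leave some of the 12 differences adjusted for age only.

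The cost is a few sentences and a small programming change; baseline HAI is already collected from all participants. The downside is small: discrete titers give uneven strata, with a median smallest group-by-stratum cell of 18 to 26 in the simulation. If nearly all baselines are at the floor, the collapsing rule applies.
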